## **Setting**

Phase I was conducted with individuals with a chronic stroke in two different outpatient clinics. Findings from this phase showed no significant differences between the focus of attention groups. These findings along with previous findings in the chronic stroke population in other studies suggest there may be more significant differences seen in those with acute stroke. Muckel and Merholz were able to show differences in performance in focus of attention in those with acute stroke during a similar weight shifting task. Based on these findings, Phase II was conducted in the inpatient rehabilitation setting.

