## **Recruitment and retention**

Twelve adults with chronic stroke (mean age  $61.4 \pm 13.8$  years; 6 months to 13 years post-unilateral stroke) with good trunk control (Function in Sitting Test mean score  $51 \pm 2.9/56$ ) were recruited for Phase I. Recruitment of participants was primarily from

\* BodiTrak. Model BT1526-8578. Vista Medical Ltd [name]

† iPad. Apple Inc. [name]

‡ Body Align Pro. serial number 86300861. Motion Unlimited Corporation California. [name].

outpatient settings, local physical therapy clinics or physician offices, located in a rural area, thus the sample size was limited.

To allow for recruitment of a larger sample than in Phase I, Phase II was conducted in an inpatient setting. Participants were recruited via staff physical and occupational therapists at the facility. Twenty-six adults post-acute stroke (mean age  $61.8 \pm 17$ , 1-10 weeks post unilateral stroke), with good trunk control (Function in Sitting Test mean score  $51.3 \pm 4.4$  out of 56) were recruited.

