### **Data analyses**

To summarize participant characteristics, descriptive data included means and standard deviations for continuous variables and counts for categorical variables. Percentages were reported to specify whether recruitment and retention goals were met based on power analysis. For Phase I, a 2 (group) X 4 (time) repeated measures mixed model ANOVA was

\* BodiTrak. Model BT1526-8578. Vista Medical Ltd [name]

† iPad. Apple Inc. [name]

‡ Body Align Pro. serial number 86300861. Motion Unlimited Corporation California. [name].

used to examine the whether the demonstration, instructions, and set up differentiated between focus of attention groups at the different timepoints of the study. Phase II utilized both a 2 (group) X 3 (time) and 2 (group) X 4 (time) mixed model ANOVA to analyze the relationship of focus of attention on performance during the different timepoints. Data including long term retention trials were examined separately due to high attrition rates. If the sphericity assumption was violated, Huynh-Feldt (H-F) and Greenhouse Geisser (G-G) corrections were used to correct the degrees of freedom to report F values. When the overall model was significant, the post hoc pairwise comparison was used, with a Bonferroni correction, to examine differences between every two timepoints in each group. Adverse events would be counted as any falls or health issues requiring medical attention such as a cardiac event.

\* BodiTrak. Model BT1526-8578. Vista Medical Ltd [name]

† iPad. Apple Inc. [name]

‡ Body Align Pro. serial number 86300861. Motion Unlimited Corporation California. [name].

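### The only stated follow-up compares timepoints within each group, so a significant group x time result has no stated contrast to show when, or by how much, the focus groups differ

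*Combined protocol and SAP*

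**What the plan says.** Under Data analyses, Phase I uses a mixed ANOVA with two groups and four timepoints to see whether the procedures "differentiated between focus of attention groups at the different timepoints of the study". Phase II uses two such models, one with three timepoints and one with four, "to analyze the relationship of focus of attention on performance during the different timepoints". The four-timepoint analysis is kept apart: "Data including long term retention trials were examined separately due to high attrition rates".

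One follow-up is described. Its condition is "When the overall model was significant". Its content is "the post hoc pairwise comparison was used, with a Bonferroni correction, to examine differences between every two timepoints in each group".

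No section names a comparison of the two groups at a given timepoint, a between-group difference in change, or an estimate or confidence interval for the focus difference. The section also does not say which F test (group, time or group x time) opens the follow-up, how many comparisons the Bonferroni correction covers, or what alpha applies.

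**The concern.** The question is put between groups and by timepoint, but the follow-up is within groups. The group main effect needs no post hoc test, because with two groups it is already a single comparison. The group x time test is different. It has 2 or 3 numerator degrees of freedom, and a significant result says only that the two profiles differ somewhere. Tests of each group's own change do not say where, or by how much.

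A within-group change also mixes focus with what both groups share. Under Procedures, everyone saw the same video after baseline, everyone practised, and everyone moved from a neutral leaning instruction to a focus instruction. Comparing two lists of within-group p-values does not remove that shared part; a between-group difference in change does.

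The unnamed trigger adds to this. If it is the interaction, the gate is sound, though the comparisons behind it are still within-group. If a time effect common to both groups can open it, the within-group tests may run when nothing suggests that the groups differ.

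**Working it through.** The plan gives no figure to reproduce: a power analysis is mentioned without inputs or result.

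**1. Count the contrasts.** Pairs of timepoints per group = t(t-1)/2. The Bonferroni levels assume alpha 0.05.

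| Model | Pairs per group | Pairs, both groups | Level, family per group | Level, one family | Between-group contrasts stated | Between-group changes from baseline (t-1) |
|---|---|---|---|---|---|---|
| 2 x 3 | 3 | 6 | 0.05/3 = 0.0167 | 0.05/6 = 0.0083 | 0 | 2 |
| 2 x 4 | 6 | 12 | 0.05/6 = 0.0083 | 0.05/12 = 0.0042 | 0 | 3 |

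The last column equals the numerator degrees of freedom of the interaction. If each group is its own family, the error over both groups can reach about 1 - 0.95 x 0.95 = 0.0975, so the undefined family matters.

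**2. Precision of the missing contrast.** Recruitment and retention gives 12 participants in Phase I and 26 in Phase II. Group sizes are not stated, so 6+6 and 13+13 are assumed, with complete data and a correlation r of 0.5-0.8 between timepoints. In SD units, the 95% CI half-width is t(0.975, 2n-2) x sqrt(2(1-r)) x sqrt(2/n).

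- Phase II, n=13: r=0.5 gives 2.064 x 1 x 0.392 = 0.81; r=0.8 gives 2.064 x 0.632 x 0.392 = 0.51.
- Phase I, n=6: r=0.5 gives 2.228 x 1 x 0.577 = 1.29; r=0.8 gives 2.228 x 0.632 x 0.577 = 0.81.
- An 11/15 split of the 26 barely changes this: 0.52-0.82.

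**3. How the fix behaves.** Simulated trials used normal, compound-symmetric data.

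- With no focus effect, Bonferroni over the 2 or 3 contrasts gives any false between-group result in 4%-5% of trials, whatever the shared gain (0 to 1 SD tried).
- If either the F test or any contrast may count as positive, the false-positive rate is about 6% (Phase II 2 x 3) and 7% (Phase I). One test must therefore carry the inference.
- Power for a true 0.5 SD difference at acquisition, with the contrasts read only after a significant interaction, is 13%-35% (Phase II 2 x 3) and 3%-9% (Phase I).

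**4. Conditional illustration of the within-group tests.** Suppose there is no focus effect, both groups gain equally, and any significant F test opens the follow-up. The table gives how often baseline-to-acquisition is significant in exactly one group, over both Bonferroni families and over paired or pooled error.

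| Shared gain | Phase II 2 x 3 | Phase I |
|---|---|---|
| 0.1 SD | 1.5%-5.0% | 0.5%-2.0% |
| 0.2 SD | 3.4%-15.3% | 0.6%-4.6% |
| 0.3-0.7 SD | 7%-50% | 1%-46% |
| 0.3-0.7 SD, interaction gate | 4% or less | 4% or less |

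The documents give no SD, correlation or gain, so these rates show a mechanism and do not estimate what happened.

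**The case against.** Three stronger readings are tempting, and the documents support none of them.

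- *The plan does not test focus.* It does: the group and group x time F tests are valid tests of it. Effects of time within each group are also a common follow-up to an interaction and suit the motor-learning question, on which Procedures reports the Phase I retention data.
- *A change significant in one group only would be taken as a focus effect.* The documents neither prescribe nor show that reading. The one focus result they report is between groups: "Findings from this phase showed no significant differences between the focus of attention groups". The higher rates in step 4 also need a sizeable shared gain and an any-F trigger.
- *The gap produced the Phase I null and so the move to acute stroke.* With 6+6 participants and a true 0.5 SD effect, neither F test is significant in 69%-84% of simulated trials. That reflects 12 participants, and a different follow-up would leave the F tests unchanged. Setting does say "Based on these findings, Phase II was conducted in the inpatient rehabilitation setting", but those findings include earlier studies, and Recruitment and retention adds another reason: "To allow for recruitment of a larger sample than in Phase I, Phase II was conducted in an inpatient setting".

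Two further limits stand. The aims listed under Study design concern feasibility and do not include effect estimation. Procedures also concedes that the Phase II instructions were too unlike each other and that the external one was mixed, so a Phase II contrast cannot be read as a pure focus effect.

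Change from baseline is not the only possible contrast. Group differences at each timepoint (3 or 4 of them) would also answer the stated question. Either is an improvement on none; change from baseline matches the interaction degrees of freedom.

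**Conclusion.** The point holds as a gap in the follow-up, and it rests on the text alone. The stated purpose is a between-group comparison by timepoint. The only follow-up is within-group, its trigger does not name an F test, its Bonferroni family is undefined, and no between-group contrast, estimate or interval appears in any section.

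Severity is minor. The main tests are sound, the study is about feasibility, and no conclusion is shown to have turned on the missing contrast. The one-group-only rates are illustrative: they apply only if a shared time effect can open the gate and the result is then read as a focus effect. They are small at a shared gain of 0.1 SD or behind the interaction gate. The interval widths assume equal groups, complete data and correlation 0.5-0.8; long-term retention intervals would be wider with fewer completers.

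**What to change.** Rewrite the follow-up paragraph under Data analyses as follows.

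- Name the group x time F test, with its alpha, as the single inferential test of focus over time.
- Replace the within-group comparisons, as the focus follow-up, with between-group differences in change from baseline at acquisition, at short-term retention and, in the four-timepoint models, at long-term retention. Report each with an estimate and 95% CI whether or not the F test is significant.
- If p-values are attached, apply Bonferroni over those 2 or 3 contrasts. Use them to locate a significant interaction, not as a second route to a positive claim.
- Keep within-group changes as a description of motor learning, and state that significance in one group only is not evidence of a focus effect.
- Label the Phase II contrast as a comparison of the instruction sets as given.

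This costs one paragraph and a re-run on existing data. The drawbacks are the wide intervals, the low power of the located contrasts, and the loss of within-group p-values as support for any focus claim.

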### **Randomization and blinding**

During Phase I, stratified randomization was used based on gender. Results from a 2013 study showed significant differences between gender during focus of attention trials suggesting the potential need for randomization based on gender. Group allocation was randomly selected for the first male and first female participants. Each following participant was alternately placed in either the internal or external focus of attention group. During Phase II, gender-based stratification was not used, to explore whether the intervention groups would naturally be comparable based on gender, age, BMI, and Function in Sitting Test scores. Instead, a blocked randomization with a random number generator (blocks of 10) was used to determine the order of focus group allocation. A blinded statistician and a graduate assistant performed the random number generation and placed the group assignments into separate envelopes, which were then sealed. Group assignment remained in sealed envelopes until after baseline measurements were completed. The participants and statistician were blinded for both phases of the feasibility study.

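### Single-step Bonferroni on all timepoint pairs is valid, but Holm's step-down version recovers part of the lost power at the same familywise error

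*Combined protocol and SAP*

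**What the plan says.** The combined protocol and SAP, Data analyses, fits a group-by-time mixed ANOVA in each phase: four timepoints in Phase I, while "Phase II utilized both a 2 (group) X 3 (time) and 2 (group) X 4 (time) mixed model ANOVA". The four-timepoint Phase II model is kept apart because of dropout: "Data including long term retention trials were examined separately due to high attrition rates".

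Pairwise tests follow only under a condition, "When the overall model was significant", and then "the post hoc pairwise comparison was used, with a Bonferroni correction, to examine differences between every two timepoints in each group". The sentence is not confined to one phase. It names no step-down version, and gives neither the significance level nor the number of tests in the Bonferroni family.

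Recruitment and retention gives the Phase II size as "Twenty-six adults post-acute stroke", with no numbers per arm. Randomization and blinding says that "a blocked randomization with a random number generator (blocks of 10) was used to determine the order of focus group allocation". Data analyses refers to "whether recruitment and retention goals were met based on power analysis", but none of the inputs or results of that power analysis appear.

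**The concern.** The pairwise tests are the only stated analysis that says which timepoints differ, for example whether acquisition or retention differs from baseline. With three timepoints there are 3 pairs per group, and with four there are 6. Single-step Bonferroni holds every pair to the strictest threshold, even after other pairs have already been rejected. With roughly a dozen people per arm, and fewer at long-term retention, that strictness costs power. Holm's procedure relaxes the threshold after each rejection and keeps the same familywise error under any dependence among the tests. What is at stake is some real within-group changes that could have been claimed at the same error rate but are not.

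**Working it through.** **Inputs from the documents.** Three or four timepoints; two groups; 26 recruited in Phase II; blocks of 10; Bonferroni over all pairs in each group. There is no stated power figure to reproduce.

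**Assumed inputs.** Two-sided familywise 0.05; family taken per group; n = 8 to 13 per arm; within-person correlation r = 0.5 to 0.8; shifts of 0.4 to 0.8 SD.

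**Numbers per arm.** 26/2 = 13, but this is not stated. If each block is 5:5 (assumed), two full blocks give 10/10 and the last 6 people come from a third block:
- 13/13: C(5,3)²/C(10,6) = 100/210 = 0.476
- 12/14: 2 × C(5,4) × C(5,2)/210 = 100/210 = 0.476
- 11/15: 2 × C(5,5) × C(5,1)/210 = 10/210 = 0.048

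One arm therefore exceeds 13 with probability of about 0.52 at randomization. Attrition then lowers the analysed numbers by an unstated amount.

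**Thresholds.** With m pairs, Bonferroni compares every p value with 0.05/m: 0.0167 for 3 and 0.0083 for 6. Holm orders the p values and compares the j-th smallest with 0.05/(m − j + 1), stopping at the first failure. For 3 pairs the steps are 0.0167, 0.025, 0.05. The first step equals Bonferroni's, so the two methods make at least one rejection in exactly the same data sets. Any gain comes from later steps.

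**One pair, exact noncentral t.** The standardized paired difference is d = shift/√(2(1 − r)). For a shift of 0.5 SD and r = 0.8, d = 0.5/0.632 = 0.79. At n = 13 and d = 0.8, power is 55.8% at 0.0167, 63.2% at 0.025 and 75.4% at 0.05.

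**All pairs, by simulation.** Paired t tests on every pair, 10,000 to 20,000 runs per scenario, Bonferroni → Holm. Means are in SD units from baseline.

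| n | Means | r | Average power per true pair | All true pairs found |
|---|---|---|---|---|
| 13 | 0, 0.5, 0.5 | 0.8 | 54% → 58% | 37% → 44% |
| 13 | 0, 0.5, 0.5 | 0.7 | 36.4% → 39.6% | 19.7% → 26.0% |
| 13 | 0, 0.8, 0.4 | 0.8 | 55% → 63% | 8% → 23% |
| 13 | 0, 0.8, 0.4 | 0.7 | 41.9% → 47.5% | 2.2% → 9.0% |
| 13 | 0, 0.8, 0.4 | 0.5 | 28% → 31% | 0.5% → 2.7% |
| 13 | 0, 0.6, 0.6, 0.6 | 0.8 | 61% → 65% | 35% → 43% |
| 8 | 0, 0.6, 0.6, 0.6 | 0.8 | 28% → 30% | 7% → 11% |
| 8 | 0, 0.6, 0.6, 0.6 | 0.5 | 8.8% → 9.4% | 0.7% → 1.4% |

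The gain in average power runs from 9.4 − 8.8 = 0.6 to 63 − 55 = 8 points. For all true pairs it runs from 1.4 − 0.7 = 0.7 to 23 − 8 = 15 points.

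**At least one difference found.** At n = 13 and r = 0.8 this was 73.0% for means (0, 0.5, 0.5), 95.0% for (0, 0.8, 0.4) and 85.0% for (0, 0.6, 0.6, 0.6), the same for both methods.

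**Familywise error.** With no true differences it was 4.3% to 4.8% for both methods. With some true differences it rose from 1.7% to 3.1% (three timepoints) and from 2.3% to 3.5% (four timepoints), still below 5%.

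**The overall-model condition.** Adding a one-group repeated-measures F test as a stand-in for the condition left the (0, 0.8, 0.4), r = 0.8 result at 55% → 63% and 8% → 23%.

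**Family size.** If the family spans both groups, m is 6 or 12 rather than 3 or 6. At n = 13 and d = 0.8, single-pair Bonferroni power falls from 55.8% to 43.4% with three timepoints (12.4 points) and from 43.4% to 32.3% with four (11.1 points). This unstated choice matters more to average power than moving to Holm.

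**The case against.** **Bonferroni is valid.** It does what it is meant to do, and choosing Holm is a choice between two valid methods. This stands, and it rules out calling the plan wrong. It does not make the methods equal: Holm never rejects fewer pairs, and the plan describes no simultaneous intervals that would be given up.

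**The larger figures depend on favourable inputs.** This also stands. The 15-point gain needs r = 0.8 and unequal shifts; at r = 0.5 the same means give 28% → 31% and 0.5% → 2.7%. The plan also sets no goal of finding every true pair.

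**Feasibility study with conditional, within-group tests.** This stands and keeps the importance low. The between-group comparison of attentional focus gains nothing.

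**The text is in the past tense and Phase I results are already reported.** A less strict correction adopted after seeing results is itself a post hoc change. That stands as a matter of labelling.

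**Stronger readings a reader might infer.** One is that Holm restores the power lost to multiplicity; its first step is identical to Bonferroni's, so it restores only part. Another is that the plan fixes 13 or fewer per arm, or thresholds of 0.05/3 and 0.05/6; the documents state neither arm sizes, alpha nor family size, and 5:5 blocks would allow 15 in one arm. A third is that the issue belongs to Phase II alone; the sentence covers both phases.

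**Conclusion.** The point holds as an optional gain in efficiency. Over the assumed ranges, Holm adds about 1 to 8 points of average power per true pair and about 1 to 15 points to the chance of finding all true pairs. It adds nothing to the chance of finding at least one difference. The ordering of the two methods and the equal familywise control are exact results; the size of the gain is not, because effect size, correlation, alpha, family size and arm sizes are all assumed. The gain does not hinge on 13 per arm: at n = 15, r = 0.7 and means (0, 0.8, 0.4), average power goes from 47.9% to 54.0%. Phase I recruited 12 people, about 6 per arm if split evenly, which lies below the range examined. Holm is equally valid there, but no figure is claimed. Label: cheap improvement.

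**What to change.** In Data analyses, for the post hoc pairwise tests of both phases, replace "with a Bonferroni correction" by: *with Holm's step-down Bonferroni correction within each group (3 pairs for three timepoints, 6 for four)*. Report Holm-adjusted p values. State the familywise alpha, and say that taking the family per group is a choice, since the document names none. With 0.05 in each group, the bound across both groups is 2 × 0.05 = 0.10.

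The cost is one phrase and no new data. Holm has no simple matching simultaneous intervals, so any Bonferroni-width intervals shown should be labelled descriptive, because they may occasionally disagree with the adjusted p values. If pairwise results have already been seen, label the Holm results as a post hoc change and show the Bonferroni results beside them.
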